1.6 What is a Quality Improvement (QI) Approach?

The QI approach is based on methodology that is grounded in operations research and management science, two well-established fields that have, for more than 90 years, combined the disciplines of statistics, psychology, systems engineering, and iterative learning, to have major impact on systems performance across countries and industries³⁵. This approach seeks to design systems for maximum effectiveness, efficiency, and adaptability and to actively disseminate the best models for health service delivery at the most rapid rate possible³⁶⁻³⁷. Specialized, evidenced-based tools aimed at rapid-cycle iterative testing of changes, networked collaborative learning, development of institutional capability for continuous improvement and frameworks to guide large-scale change have been developed³⁸⁻⁴⁰ to facilitate this process (Figure 1). The QI approach supports a shift in provider attitudes and practice from a prescriptive mode to one that supports critical thinking and problem solving skills with continuous review and improvement of service provision.

[figure not shown]

Figure 1: Model for improvement

Health care quality improvement principles and the Model for Improvement (Figure 1) provide an effective approach to help close the gap between evidence-based knowledge and the ability of health systems to implement large-scale programs^{35, 37}. This approach places a premium on data driven front line decision-

making, peer-to-peer knowledge exchange, local adaptation of clinical protocols, and highly participative management ⁴¹. Originally developed in the United States and widely adopted in the United Kingdom and other high-income nations, these efforts have increasingly found their way, with appropriate modifications, into global health applications in low and middle income countries ⁴²⁻⁴³.

Application of the QI approach to health systems of low and middle income countries shows considerable promise. Efforts in the Russian federation have reduced neonatal mortality by 60% ⁴⁴; in Niger, malnutrition-related fatality was halved in a single year ⁴⁵; in Ecuador, an essential obstetric care collaborative substantially reduced the incidence of post-partum hemorrhage ⁴⁶; in projects in South Africa, rapid scale-up of access to HIV care and treatment services and falling rates of mother-to-child transmission of HIV at a district level have been demonstrated ⁴⁷⁻⁴⁸.

Traditionally this approach is used following policy formulation and where some program implementation experience has already been established. This often means that health care providers have to unlearn what they have been doing for years and replace with new enabling and empowering approaches that involve critical thinking and problem solving skills, which have the added advantage of application to other health challenges facing the facility or service. CAPRISA 008 will be testing this model in a rigorous manner through strengthening existing family planning services as a foundation to introduce a new health technology even prior to licensure and importantly pave the way for more rapid, efficient, safe and effective access to a much needed product to women who would benefit most. A strengthened family planning service and more engaged providers will benefit existing family planning services, overall health care delivery in these facilities and most importantly support and benefit the clients of these services. .

2. STUDY GOAL AND OBJECTIVES

2.1 Primary objective

To assess the effectiveness of an implementation model which integrates tenofovir gel provision into existing family planning services

2.2 Secondary objectives

To compare women receiving tenofovir gel through family planning services with women receiving tenofovir gel through clinical trial clinics for the following:

1. Safety of tenofovir gel measured by clinical and laboratory adverse event rates, including pregnancy rates and outcomes
2. HIV incidence rates
3. The estimated proportion of reported sex acts covered by two gel doses, self-reported adherence to the tenofovir gel dosing strategy and factors influencing gel use in relation to sexual activity, condom use, and intravaginal practices
4. Self-reported service acceptability and completion rates of quarterly (or 2 monthly in Nur-isterate users) HIV and pregnancy testing
5. HIV viral load among HIV seroconverters
6. Tenofovir resistance of HIV strains from HIV seroconverters
7. Vaginal cytokines to assess the role of genital inflammation in HIV acquisition
8. HSV-2 and HPV incidence rates
9. Tenofovir levels
10. Self-reported product acceptability

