Provision of tenofovir gel and study monitoring for women enrolled in the intervention arm will be done through local family planning services where QI methodology will be used to promote reliable delivery of tenofovir gel and family planning services. Participants in the intervention arm will have monthly visits for the first three months post-enrollment; thereafter, gel provision and monitoring will be scheduled to coincide with each participant's routine family planning visit (typically every 2-3 months). Study visits in the intervention arm will be scheduled no longer than 3 months apart.

Women assigned to the control arm will have monthly scheduled visits at the CAPRISA urban or rural clinic where they will be provided with 1% tenofovir gel.

HIV and pregnancy testing will be performed at each study visit in both study arms. HIV/sexually transmitted infection (STI) risk reduction messages and condoms will be provided to all participants using consistent prevention messages. Similarly, family planning services, tenofovir gel and counseling on product adherence will be provided to all participants. Participants in both study arms will be requested to return all used and unused applicators at each study visit.

Clinical safety will be assessed pre-, during- and post-enrollment. Laboratory safety assessments will be done at enrollment, months 6, 12, 18, 24, study exit and additionally if indicated. At these visits, blood samples will be collected for urea, electrolytes, creatinine, liver function tests, full blood count, calcium and phosphate levels. Pelvic examinations, including naked eye examination of the external genitalia and speculum examination of the vagina and cervix will be conducted at enrollment, months 6, 12, 18, 24, study exit and additionally if indicated. These visits will also include collection of blood for storage of serum and plasma and genital specimens for storage to assess for markers of safety, risk exposure, product adherence, potential post-trial assessments of activity against STIs, and tenofovir resistance. For symptoms experienced between scheduled visits, the participant will be counseled to report to their assigned study site as soon as possible.

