7.3 Follow-up visits

Women randomized to the intervention arm will attend monthly visits for the first 3 months of study participation. Thereafter, gel provision and monitoring will be scheduled to coincide with each participant’s

routinely scheduled family planning visits (typically every 2-3 months). Follow-up visits for women enrolled into the control arm are scheduled throughout the study follow-up period on a 28-day schedule. The visit window around a study visit is 14 days on either side. In addition to the regular follow-up requirements, additional procedures are done at study months 6, 12, 18, 24 and study exit for all participants. For participants who do not complete scheduled visits within the allowable window, the visit will be considered “missed” and relevant CRFs will be completed to document the missed visit. However, for participants who miss their month 6, 12, 18 or 24 visits, the study procedures specified to take place at these visits will be conducted at the participants’ next visit.

Participants who become pregnant during the study will be followed as usual, but gel will be withheld until they have a negative pregnancy test. For participants who become HIV infected during the study, product will be permanently discontinued once diagnosis of a HIV positive status is confirmed. HIV seroconvertors in the trial will be referred to the CAPRISA 002 Acute Infection study and/or the CAPRISA 009 treatment study for further care and follow-up. For women opting not to enroll in the CAPRISA 002 or CAPRISA 009 study they will be referred to the CAT Programme at the urban or rural site as appropriate or to other sources of care and support available to these communities.

Follow-up study visits occur monthly for the first 3 months and 2-3 monthly thereafter up to and including the study exit visit for participants in the intervention arm and monthly up to and including the study exit visit for participants in the control arm. The following study procedures will be performed during study follow-up:

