7.3.2 Clinical procedures

- Interval (i.e. since last visit) medical and menstrual history including detailed intermenstrual bleeding history and AE assessment and concomitant medication review
 - Each study visit
 - Additionally when indicated
- Pelvic examination
 - At months 6, 12, 18, 24 and study exit
 - Additionally when indicated
- Genital specimen collection
 - At months 6, 12, 18, 24 and study exit
 - If indicated, at the time of suspected or confirmed HIV seroconversion
- Blood draw
 - At months 6, 12, 18, 24 and study exit
 - Additionally when clinically indicated

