9.2.2 Secondary endpoints

The following secondary endpoints will be assessed:

- Clinical and laboratory adverse event and pregnancy rates
- HIV incidence rates.
- Self-reported adherence to the tenofovir gel dosing strategy (and factors influencing gel use in relation to sexual activity, condom use, and intravaginal practices)
- Self-reported service acceptability and completion rates of quarterly HIV and pregnancy testing
- HIV viral load among HIV seroconverters.
- Tenofovir resistance among HIV seroconverters.
- Vaginal cytokines.
- HSV-2 and HPV incidence rates
- Tenofovir levels (and their correlation with HIV and HSV-2 infection rates)
- Self-reported product acceptability.

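### Clinical adverse event rates are compared between arms, but after month 3 control women are asked about events two to three times as often, so minor events are likely to be under-recorded in the family planning arm

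*Protocol*

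**What the plan says.** Section 2.2 lists, as the first item to be compared between women served by family planning clinics and women served by the research clinics, "Safety of tenofovir gel measured by clinical and laboratory adverse event rates, including pregnancy rates and outcomes". Section 9.2.2 carries this into the endpoint list as "Clinical and laboratory adverse event and pregnancy rates".

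Section 7.3.2 ties clinical AE collection to the visit. At each study visit staff take an "Interval (i.e. since last visit) medical and menstrual history including detailed intermenstrual bleeding history and AE assessment", with further enquiry when indicated.

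The visit schedules differ by arm:

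- Control: section 3.1 states "Women assigned to the control arm will have monthly scheduled visits at the CAPRISA urban or rural clinic", and section 7.3 says that these visits "are scheduled throughout the study follow-up period on a 28-day schedule".
- FP: section 3.1 states "Participants in the intervention arm will have monthly visits for the first three months post-enrollment". Visits then follow the routine family planning schedule, typically every 2-3 months, and "Study visits in the intervention arm will be scheduled no longer than 3 months apart". The comparison table in section 5 gives 3-monthly visits, or 2-monthly for women on one named injectable contraceptive.

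Laboratory safety tests are on a common schedule: "Laboratory safety assessments will be done at enrollment, months 6, 12, 18, 24, study exit and additionally if indicated". Sections 3.1 and 7.3.2 put the scheduled pelvic examinations at the same months.

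**The concern.** Visit frequency is part of the intervention being tested, so its effect on gel use belongs in the primary comparison. Its effect on AE recording is a different matter. How often a woman is asked changes what is written down, not what happened to her. A longer recall period can lose events that a shorter one would have caught, so the plausible direction is a lower recorded rate in the FP arm.

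Section 1.5 says that evidence is needed on whether integrated provision reaches levels of safety similar to those of the earlier trial. An FP rate that is low only because of recall would give unearned reassurance on that point. It might also go unnoticed during the trial, because section 8.4 describes the interim monitoring reviews as pooled across arms.

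**Working it through.** The protocol gives no figure for this comparison, so there is none to reproduce. The check counts enquiries and then shows what unequal recall could do.

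**1. Scheduled enquiries per woman.** Inputs are a 28-day interval in control (section 7.3) and, in FP, three monthly visits followed by 2- or 3-monthly visits (sections 3.1 and 5). Accrual of about 12 months and follow-up of about 18 months after accrual ends (section 3.1) give 18 to 30 months per woman. One month is taken as 30.4375 days, and counts are rounded down.

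- 24 months, control: 24 × 30.4375 / 28 = 26.1, so 26.
- 24 months, FP 3-monthly: 3 + 21/3 = 10. FP 2-monthly: 3 + 21/2 = 13.5, so 13.
- 18 months: 19 against 8 (3-monthly) or 10 (2-monthly).
- 30 months: 32 against 12 or 16.

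Control women are asked between 19/10 = 1.9 and 32/12 = 2.7 times as often.

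**2. Illustrative effect on recorded rates.** Assume equal true rates. Assume also that an event t days before the next visit is reported with probability 2^(−t/h), where h is a recall half-life. The documents give no value for h. Average capture over an interval of L days is

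R(L, h) = (1 − 2^(−L/h)) / (ln 2 × L/h).

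Control capture is R(28, h). FP capture over 24 months is [3 × R(30.4, h) + 21 × R(30.4m, h)] / 24, with m = 2 or 3. The recorded rate ratio is FP capture divided by control capture.

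- Low end (h = 30 days, 3-monthly): R(28) = 0.736, R(30.4) = 0.718, R(91.2) = 0.417. FP = (3 × 0.718 + 21 × 0.417)/24 = 0.455. Ratio = 0.455/0.736 = 0.62.
- High end (h = 365 days, 2-monthly): R(28) = 0.974, R(30.4) = 0.972, R(60.8) = 0.944. FP = (3 × 0.972 + 21 × 0.944)/24 = 0.948. Ratio = 0.948/0.974 = 0.97.

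| Assumed half-life (days) | FP/control, 2-monthly | FP/control, 3-monthly |
|---|---|---|
| 30 | 0.76 | 0.62 |
| 90 | 0.90 | 0.82 |
| 180 | 0.95 | 0.90 |
| 365 | 0.97 | 0.95 |
| no recall loss | 1 | 1 |

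If half of all events are always captured, because they are serious or are reported between visits, the ratios rise to 0.90 / 0.84 (30 days), 0.95 / 0.92 (90 days) and 0.97 / 0.95 (180 days).

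**3. Would a modest distortion show?** Section 9.3 gives 350 women per arm and 10% loss, so 315. With 24 months each, that is 630 woman-years. At the 3.55 events per woman-year in the gel arm of the earlier trial (section 1.3), 630 × 3.55 = 2,237 events. For an artefactual ratio of 0.90, the Poisson standard error of the log ratio is √(1/2,237 + 1/(0.9 × 2,237)) = 0.031, against |ln 0.90| = 0.105. The chance of a nominal two-sided 5% result is then about 93%. With threefold overdispersion the standard error is 0.053 and the chance about 51%. This is for scale only. The 3.55 is not limited to clinical events, the overdispersion is assumed, and the protocol names no test for AE rates.

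**The case against.** The strongest reply is that no follow-up time goes unasked. The interval history covers the whole period since the last visit, and the protocol provides several routes between visits. Section 3.1 has women counselled to report symptoms promptly, section 8.2 gives them telephone numbers and tells them to report AEs, section 7.4 allows interim visits for AEs, and section 5 repeats the advice at each visit in both arms. All of this stands. It confines the problem to events that are both forgotten and never self-reported. It does not make active elicitation equal.

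A second reply is that section 9.5 leaves the analysis of secondary objectives to the SAP, which is not at hand and may already restrict the comparison. That is possible. The unequal collection, however, is fixed in the protocol, and section 9.2.2 names clinical AE rates without limitation.

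A reader might also infer more than the documents support:

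- That mild, self-limiting events make up most of the AEs. Section 1.3 describes one category that way (diarrhea and gastrointestinal infections) and gives no severity breakdown of the total.
- That completion of quarterly testing (secondary objective 4) is distorted in the same way. The protocol states no scoring rule for it, so there is nothing to fault.
- That pregnancy outcomes are biased through missed early losses. Pregnancy tests do follow the visit schedule, but the documents give nothing from which to judge such an effect.

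**Conclusion.** The point holds as a caution about one secondary comparison. By design, clinical AEs are ascertained about 2.0 to 2.6 times as often in control over 24 months, with the imbalance starting after month 3. The likely direction is under-recording in the FP arm.

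The size cannot be derived from the documents. The range of 0.62 to 0.97 rests on an assumed exponential recall loss with half-lives of 30 to 365 days, applied to every event. It moves towards 1 as more events are captured regardless of the interval.

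It would be tempting to say that the FP arm is bound to look safer, or to express the artefact as a fixed number of standard errors. Neither is supported, since any such number only restates the recall loss that was assumed. Nor does the problem extend to all safety data. Scheduled laboratory and pelvic findings share a schedule, and serious events are unlikely to be forgotten. The primary endpoint is gel use, and this point does not touch it.

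**What to change.** In section 9.2.2, with matching text in the SAP:

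- Base the between-arm safety comparison on laboratory abnormalities and scheduled pelvic findings at months 6, 12, 18, 24 and exit, where both arms share a schedule.
- Add serious and grade 3-4 events as outcomes that depend less on recall, and note that they are not collected on an identical schedule. Severity is already graded under section 8.2.
- Report all other clinical AE rates by arm descriptively, with the number of assessments per woman and a statement that ascertainment differs by arm.

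This is a change of wording only. It needs no new data and no change to visits or care. The price is fewer events in the comparison, and so less precision.

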3. METHODS

3.1 Study overview

This is a two-arm, open-label, randomized, controlled trial. A maximum of 700 sexually active, HIV-uninfected women aged 18 years and older who previously participated in an ARV prevention study will be enrolled from an urban and rural site in KwaZulu-Natal. The study's Data and Safety Monitoring Board (DSMB) will monitor the parameters used to estimate the sample size and may, if needed, recommend changes, during the study, in the sample size and/or follow-up duration. The primary endpoint of gel use will be assessed as the mean number of returned used applicators per participant per month. The sample size is estimated to provide 90% power to demonstrate whether gel use in women attending family planning services is similar, but no more than 20% lower than, gel use among women attending the CAPRISA research clinics, stratified by study population and adjusted for 10% loss to follow-up. Safety will be

assessed by the frequency of adverse events using laboratory and clinical markers. While this study is not specifically designed to use HIV incidence rates to assess non-inferiority of the family planning clinic arm, HIV incidence rates observed in the trial as a secondary endpoint will be used to assist in the interpretation of the primary outcome of the trial. The acceptability of family planning services for tenofovir provision will be assessed using self-report and clinic attendance rates.

The anticipated total study duration is approximately 30 months, with accrual requiring approximately 12 months and follow-up continuing for approximately 18 months after the end of the accrual period. Potential study participants will be screened for eligibility and eligible participants will be enrolled in the study within 30 days of screening. At each of the two sites, consenting eligible participants will be randomly assigned to receive 1% tenofovir gel through either family planning services (intervention arm) or the CAPRISA clinics (control arm) at both study sites.

Provision of tenofovir gel and study monitoring for women enrolled in the intervention arm will be done through local family planning services where QI methodology will be used to promote reliable delivery of tenofovir gel and family planning services. Participants in the intervention arm will have monthly visits for the first three months post-enrollment; thereafter, gel provision and monitoring will be scheduled to coincide with each participant's routine family planning visit (typically every 2-3 months). Study visits in the intervention arm will be scheduled no longer than 3 months apart.

Women assigned to the control arm will have monthly scheduled visits at the CAPRISA urban or rural clinic where they will be provided with 1% tenofovir gel.

HIV and pregnancy testing will be performed at each study visit in both study arms. HIV/sexually transmitted infection (STI) risk reduction messages and condoms will be provided to all participants using consistent prevention messages. Similarly, family planning services, tenofovir gel and counseling on product adherence will be provided to all participants. Participants in both study arms will be requested to return all used and unused applicators at each study visit.

Clinical safety will be assessed pre-, during- and post-enrollment. Laboratory safety assessments will be done at enrollment, months 6, 12, 18, 24, study exit and additionally if indicated. At these visits, blood samples will be collected for urea, electrolytes, creatinine, liver function tests, full blood count, calcium and phosphate levels. Pelvic examinations, including naked eye examination of the external genitalia and speculum examination of the vagina and cervix will be conducted at enrollment, months 6, 12, 18, 24, study exit and additionally if indicated. These visits will also include collection of blood for storage of serum and plasma and genital specimens for storage to assess for markers of safety, risk exposure, product adherence, potential post-trial assessments of activity against STIs, and tenofovir resistance. For symptoms experienced between scheduled visits, the participant will be counseled to report to their assigned study site as soon as possible.

Participants identified with an STI or other treatable reproductive tract infection at a scheduled or participant-initiated visit will be provided counseling and clinical care at the study sites in accordance with the South African Department of Health guidelines. Participants with STIs will be encouraged to refer their partners for treatment.

While contraceptive services will be provided to all CAPRISA 008 participants, those who become pregnant during the study will discontinue product use while they are pregnant. Pregnant women will be advised to continue with their follow up visits. When these participants no longer have a positive pregnancy test, the pregnancy outcome will be documented and they will be re-started on tenofovir gel should they wish to continue with study participation.

Participants infected with hepatitis B virus (HBV) at enrollment will be closely monitored clinically and using laboratory diagnostics especially during episodes of product hold. Any participant needing further treatment for HBV will be referred to a health care provider for further follow-up.

Participants who become HIV infected during study follow-up will be referred to the CAPRISA Acute Infection Study (CAPRISA 002), the CAPRISA Treatment Study (CAPRISA 009) and/or the CAPRISA AIDS Treatment (CAT) Programme for ongoing care, antiretroviral treatment and follow-up. Participants who do not wish to enroll in CAPRISA studies will be provided with information on other sources of care and support available in the community or appropriate health facilities serving the catchment populations.

